## 8.4 UNANTICIPATED PROBLEMS

### 8.4.1 DEFINITION OF UNANTICIPATED PROBLEMS

This protocol uses the definition of Unanticipated Problems as defined by the Office for Human Research Protections (OHRP). OHRP considers unanticipated problems involving risks to participants or others to include, in general, any incident, experience, or outcome that meets all of the following criteria:

- Unexpected in terms of nature, severity, or frequency given (a) the research procedures that are described in the protocol-related documents, such as the Institutional Review Board (IRB)-approved research protocol and informed consent document; and (b) the characteristics of the participant population being studied;
- Related or possibly related to participation in the research (“possibly related” means there is a reasonable possibility that the incident, experience, or outcome may have been caused by the procedures involved in the research); and
- Suggests that the research places participants or others at a greater risk of harm (including physical, psychological, economic, or social harm) than was previously known or recognized.]

### 8.4.2 UNANTICIPATED PROBLEMS REPORTING

UPs that are serious adverse events will be reported as indicated in section 8.3.4. > 1.1.3 and any other UP will be reported to the IRB and the funding agency as indicated in section 8.3.4. > 1.1.2. The investigator will report unanticipated problems to the IRB and will include the following information:

- Protocol identifying information: protocol title and number, PI's name, and the IRB project number
- A detailed description of the event, incident, experience, or outcome
- An explanation of the basis for determining that the event, incident, experience, or outcome represents an UP
- A description of any changes to the protocol or other corrective actions that have been taken or are proposed in response to the UP

#### 8.4.3 REPORTING UNANTICIPATED PROBLEMS TO PARTICIPANTS

N/A

## 9 STATISTICAL CONSIDERATIONS

### 9.1 STATISTICAL HYPOTHESES

- Primary Endpoint(s):

Hypothesis 1: Noom Health users will show 6 month efficacy relative to Noom Digital Health for weight loss at post-intervention.

Hypothesis 2: Noom Health users will show long-term (12 Month) efficacy relative to Noom Digital Health.

- Secondary Endpoint(s):

Hypothesis 1: Clinical Profile (composite moderator) will show significant interaction with treatment condition, demonstrating that individuals with a more severe profile (older, less support, more health conditions, more psychosocial problems) will benefit more from Noom Health than Noom Digital Health.

Hypothesis 2: Weight suppression (absolute difference between highest and current weight) will moderate efficacy of Noom Health vs. Noom Digital Health.

### 9.2 SAMPLE SIZE DETERMINATION

Mt. Sinai will use piecewise latent growth curve models with treatment as primary indicator. Using Monte Carlo simulation studies with 10,000 draws and 6 time points and 2 growth processes, Mt. Sinai evaluated sample size needed to detect significant differences on each growth process (within treatment, post-treatment follow-up). Mt. Sinai also varied missing at random patterns of missing of data at 10%, 20% and 30% increasing linearly over each timepoint. The results indicate that with 30% missing data, mean difference in BMI change of 1.2 (SD =4.5), Mt. Sinai is 85% powered to detect significant difference at 24 month follow-up with N = 600. The power increases substantially for within treatment BMI change .8 (SD =4.5), power = .942. For psychosocial outcomes, N=600 with same parameters indicated 82-90% power to find treatment effects at 24 months, assuming a .20 SD unit difference between groups. Within treatment, the same difference is powered 90-98%.

For Aim 2, Mt. Sinai assumed full information on all moderators and tested the interaction effect with a composite moderator profile of 12 indicators. The interaction between latent moderator (M) and treatment was powered at .93 and .85 with N=600, and 30% attrition for within treatment and follow-up.

For Aim 3 power analyses were based on a 13-item adherence measure adapted from the Noom Monitor (Binge Eating) study and assumes network efficiency of .75. Mt. Sinai would examine the relationship between network entropy and the outcomes, with statistical power for the regression prediction at 100% for each outcome. Mediation model of weekly regular eating is a time series mediation model and assumes latent measure of meal-snack adherence will mediate changes in weight. The calculation is based on effect size goal of .25, .5, and .75. The results of simulations suggest that power for the smallest effect size (.25) is approximately .80 with 10% missing data or less and moderate correlations between time and change in regular eating (.3) and moderate correlation between regular eating and weight outcome (.3).

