### 9.4 STATISTICAL ANALYSES

#### 9.4.1 GENERAL APPROACH

We are using a latent growth curve model (piecewise) to model separate change processes assumed during weight loss and post intervention. All models will be examined for goodness of fit, normality and linear (vs. Nonlinear) change. Best fit models will be interpreted for primary effects.

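### Primary Hypothesis 2 (efficacy at 12 months) has no stated 12-month contrast, and the two growth-process effects that the plan describes cannot test both primary hypotheses

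*Combined protocol and SAP*

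**What the plan says.** Section 9.1 sets two primary hypotheses, each tied to a time point: "Hypothesis 1: Noom Health users will show 6 month efficacy relative to Noom Digital Health for weight loss at post-intervention" and "Hypothesis 2: Noom Health users will show long-term (12 Month) efficacy relative to Noom Digital Health". Section 3 repeats them.

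Section 9.4.1 names the model, a "latent growth curve model (piecewise) to model separate change processes assumed during weight loss and post intervention", and says that the best-fitting version will be read for the primary effects. Section 9.4.2 applies the same model to weight and to the psychosocial and health endpoints. Neither section names a parameter, a contrast, a time coding or a knot month, and neither links Hypothesis 1 or 2 to a test.

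Section 9.2 comes closest to naming tested effects, and it names two kinds:
- Arm differences by phase: the simulation "evaluated sample size needed to detect significant differences on each growth process (within treatment, post-treatment follow-up".
- Differences at a time point, all at 24 months: "Mt. Sinai is 85% powered to detect significant difference at 24 month follow-up with N = 600" for BMI, and "82-90% power to find treatment effects at 24 months, assuming a .20 SD unit difference between groups" for psychosocial outcomes.

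No 12-month effect is defined or powered anywhere.

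**The concern.** In a piecewise growth model, the arm effect on the second segment describes how the arms move relative to each other after the knot. It does not say how far apart they are at a given visit. Hypothesis 2 asks how far apart they are at month 12.

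The gap matters because Sections 4.1 and 6.1.2 make holding the lost weight the aim of the second six months. If the intervention does exactly that, and the control arm also holds, the arms differ at month 12 and the post-month-6 effect is nil. The same fitted model can therefore support opposite answers on a primary hypothesis, depending on which quantity is read from it. The plan leaves that choice open until the data are in hand.

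**Working it through.** **Notation.** D(t) is the arm difference in BMI change from baseline at month t, positive when Noom Health has lost more. b1 and b2 are the arm effects on the first and second slopes, per month.

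**Inputs from the documents.** 300 per arm (4.1); visits at months 0, 1, 4, 6, 12, 18, 24 and 30 (1.3); "with 30% missing data, mean difference in BMI change of 1.2 (SD =4.5" for follow-up and "within treatment BMI change .8 (SD =4.5), power = .942" (both 9.2). Alpha and sidedness are not stated, so two-sided 5% is assumed.

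**Step 1: the plan's 85%.** Power = Φ(δ/SE − 1.96), with SE = SD·√(2/n). Let missingness rise linearly from 0 to 30%, averaging 15%, so n = 255 per arm. Then SE = 4.5·√(2/255) = 0.399, and 1.2/0.399 − 1.96 = 1.05, which gives 85.3%. With 300 per arm the result is 90.4%, and with 210 it is 78.0% (86.2% if one-sided). The 85% is thus consistent with a plain difference in change at 24 months. The companion .942 does not reproduce this way: two-sided power for 0.8 is 44.5% (210 per arm) to 58.6% (300 per arm), and one-sided power is at most 70.3%. That figure comes from a growth-model simulation whose variance inputs are not given, and nothing below rests on it.

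**Step 2: knot at month 6.** D(6) = 6·b1 and D(12) = 6·b1 + 6·b2.
- Maintained advantage, D(12) = D(6): b2 = 0. The second-process test rejects 5% of the time, 2.5% in favour of Noom Health, at any sample size.
- Larger loss, faster regain, for example D(6) = 1.2 and D(12) = 0.8: 6·b2 = −0.4. The second process favours control while Noom Health is still 0.8 ahead.

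**Step 3: knot at month 12.** With a linear first segment, D(6) = 6·b1 and D(12) = 12·b1, so D(6) = D(12)/2. Estimate and standard error are both halved, the test statistic is identical, and Hypotheses 1 and 2 are one test. The second process starts after month 12 and bears on neither.

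**Step 4: power of a month-12 contrast, maintained 0.8, knot at month 6.** SE² = 36·[Var(b1) + Var(b2) + 2·Cov(b1, b2)], from the generalised least squares information matrix with eight visits and monotone dropout rising linearly to 30% at the last visit. The variance components are assumptions: intercept SD 5, residual SD 1.0, independent random effects.
- SD of 6-month change held at the plan's 4.5, and post-month-6 slope SD of 0.5, 1.0 or 2.0 BMI units per six months: SE = 0.376, 0.384, 0.415. Power = Φ(0.8/SE − 1.96) = 57%, 55%, 49%. For a maintained 1.2, power is 89%, 88%, 82%.
- Variance placed mainly after month 6 (first-segment SD 1.5, second-segment SD 1.35 per six months): 24-month change SD = √(1.5² + 9·1.35² + 2·1.0²) = 4.5. SE = 0.197, and Φ(0.8/0.197 − 1.96) = 98%. This split also gives about 85% for 1.2 at month 24.

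Hence the range of roughly 50-98%.

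**Step 5: an effect that keeps growing.** Take 0.8 at month 6 and 1.2 at month 24, reading 1.2 as cumulative. The second process gains 0.4/3 = 0.133 per six months, and D(12) = 0.933. For slope SDs 0.5, 1.0 and 2.0, the second-process test has 69%, 28% and 11% power, and the month-12 contrast has 70%, 68% and 61%. With slope SD 0.4 the order reverses (second-process SE 0.047, 82% against 70%). So the power comparison does not always favour the month-12 contrast. What never changes is that the two tests answer different questions.

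**The case against.** The strongest reply is that a sample-size paragraph is not a decision rule. Section 9.2 reports what a simulation looked at. Section 9.1 states the hypothesis at month 12, and a month-12 difference can be obtained from the model in 9.4. Time coding is also unstated, and a suitable centring makes a model term equal to a difference at a visit.

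This stands as far as it goes, and it rules out two stronger readings. A reader might infer that a maintained advantage would be declared a failure on Hypothesis 2. The documents do not support that, because no section assigns Hypothesis 2 to the second process. A reader might also infer that process differences are the only effects named. They are not: 9.2 also names differences at 24 months, and the 85% reproduces as one.

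A second reply is that the knot may be at month 12. Section 4.1 describes the two six-month periods together as a year of intervention, and the schedule in 1.3 marks the interventions through the day-365 visit. On that reading the first-process effect is the 12-month difference, and Hypothesis 2 has a valid test. This is correct, but Hypothesis 1 then has no test of its own (Step 3).

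Third, the power figures depend on assumed variance components. That also stands. The upper end gives up the plan's SD of 4.5 for within-treatment change. On the other hand, the plan's own .942 for 0.8 implies SE = 0.8/(1.96 + 1.57) = 0.227, or an effective SD near 2.8 at 300 per arm, so the documents do not settle where in the range the truth lies. The 5% rejection rate is simply the size of a test whose null is true; it illustrates the mismatch and does not predict this trial's result.

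Finally, post-treatment divergence is a legitimate question, given the interest in durability in 4.2. It need not be dropped.

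**Conclusion.** The concern holds in a conditional form. The plan names no knot and no 12-month contrast, and under neither plausible knot do the two process effects test both primary hypotheses. The algebra for this needs no variance assumption; the 12-month-knot result needs only a linear first segment. The harm is possible rather than certain: if Hypothesis 2 were judged on the second process with a 6-month knot, a real and maintained 12-month benefit could be missed, or the sign reversed. For a maintained 0.8 BMI difference the choice is between a 5% rejection rate and roughly 50-98% power, the latter resting on the assumed variance split, dropout pattern and two-sided 5% level. Because this concerns the test of a primary hypothesis, it should be settled before anyone analyses outcome data by arm.

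**What to change.** In 9.1 and 9.4.2:
- State the knot. Month 6 lets the month-6 and month-12 differences be estimated separately.
- Define the test of Hypothesis 1 as the model-implied arm difference in change from baseline at month 6, and that of Hypothesis 2 as the same quantity at month 12.
- Give the month-12 quantity explicitly: the sum over segments of arm effect times elapsed time, here 6·b1 + 6·b2, with a standard error from the joint covariance matrix. If fit checks lead to extra segments or curvature, the contrast is still the model-implied difference at month 12.
- Keep single-process effects, if wanted, as secondary evidence on durability, but not as the test of Hypothesis 2.

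In 9.2, add power for the month-12 contrast and state alpha, sidedness and the variance inputs.

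The cost is a few sentences, one linear contrast from the same fitted model and a rerun of the existing simulation for month 12. No new data, visits or participants are needed.

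### Section 9.2: the stated 82-90% power for a 0.20 SD psychosocial difference at 24 months does not follow from the printed inputs, and no power is stated for month 12

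*Combined protocol and SAP*

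**What the plan says.** Section 9.2 bases N=600 on simulations of a piecewise latent growth model: "Using Monte Carlo simulation studies with 10,000 draws and 6 time points and 2 growth processes". On missing data: "Mt. Sinai also varied missing at random patterns of missing of data at 10%, 20% and 30% increasing linearly over each timepoint". For BMI with 30% missing it reports: "mean difference in BMI change of 1.2 (SD =4.5), Mt. Sinai is 85% powered to detect significant difference at 24 month follow-up". The next sentence reads: "The power increases substantially for within treatment BMI change .8 (SD =4.5), power = .942". For psychosocial outcomes N=600 is described as "with same parameters indicated 82-90% power to find treatment effects at 24 months, assuming a .20 SD unit difference between groups", followed by "Within treatment, the same difference is powered 90-98" (per cent).

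The section does not state alpha or sidedness, correlations between visits, growth-factor variances, whether 4.5 is the SD of BMI or of BMI change, or which SD the 0.20 refers to.

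In Section 9.1 the first primary hypothesis is "Noom Health users will show 6 month efficacy relative to Noom Digital Health for weight loss at post-intervention"; the second concerns efficacy at 12 months. Section 9.4.2 analyses weight and psychosocial/health outcomes as primary endpoints with one and the same model.

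**The concern.** At one time point, with one sample size and one set of parameters, a standardised effect a quarter smaller (0.20 against 0.267) is credited with similar or higher power. With equal precision that cannot happen. This paragraph is the plan's only statement of what 600 participants can detect on weight and psychosocial outcomes. If a psychosocial result is null, readers will weigh it against 82-90% power. They also cannot see what was detectable at month 12, a primary time point. The planned estimates and confidence intervals are not affected.

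**Working it through.** **Inputs.** 300 per arm (Section 4.1). From Section 9.2: 1.2 with SD 4.5 and 85% at 24 months, 30% missing; 0.20 SD and 82-90% at 24 months; 0.8 with SD 4.5 and .942 within treatment; missingness 10, 20 and 30%. Assumed: two-sided 5%; monotone dropout reaching the named percentage at the last visit; information proportional to the fraction retained.

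**1. Reproduce the 85%.** 1.2/4.5 = 0.267. A two-sample t test has 90.3, 85.2 and 77.8% power at 300, 255 and 210 per arm. The 85% is therefore plausible and is taken as given.

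**2. Carry that precision to 0.20 SD.** Noncentrality for 85%: 1.960 + 1.036 = 2.996. Scaled: 2.996 × 0.20/0.2667 = 2.247. Power = Φ(2.247 − 1.960) = 61.3% at the same 30% missing. With other error rates: 64% (one-sided 5%), 55% (two-sided 1%).

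**3. Allow for less missing data.** Noncentrality = 2.247 × √((1 − m)/0.70).

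| Missing at last visit | Noncentrality | Power for 0.20 SD |
|---|---|---|
| 30% | 2.247 | 61% |
| 20% | 2.402 | 67% |
| 10% | 2.548 | 72% |
| 0% | 2.686 | 77% |

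Under monotone dropout at least 70% have complete data, so information can rise by at most 1/0.70; 77% is an upper bound.

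**4. Reverse check.** 82% and 90% need noncentralities of 2.875 and 3.242. Divided by 0.75 these become 3.834 and 4.322, i.e. 97% and 99% power for 0.267 SD, not 85%.

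**5. What would reconcile the figures.**

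(a) Smaller psychosocial variances. With both effects in the same SD unit and 30% missing, the psychosocial contrast needs (2.247/2.875)² = 0.61 times the BMI contrast variance for 82%, and (2.247/3.242)² = 0.48 for 90%. If the 90% belongs to 10% missing, the ratio is (2.548/3.242)² = 0.62.

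(b) A larger SD unit. An analytic piecewise growth model was run with assumed inputs: 300 per arm, equal baseline means, visits at 0, 1, 6, 12, 18 and 24 months, knot at month 6, baseline SD 4.5, intercept share 0.81 of baseline variance, and independent random-slope SDs of 1.23 (treatment) and 3.5 (after treatment). Its 24-month SD is 5.83, so 0.20 SD is 0.20 × 5.83 = 1.17 BMI units, close to 1.2.

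| Quantity | Model | Section 9.2 |
|---|---|---|
| 1.2 at 24 months, 30% missing | 85.5% | 85% |
| 0.8 within treatment, 30% missing | 94.5% | 94.2% |
| 0.20 × 5.83 at 24 months, 30 / 20 / 10% missing | 83 / 87 / 89% | 82-90% |
| 0.20 × 4.5 at 24 months, 30% missing | 62% | – |
| 0.20 SD within treatment | about 98.6-99% | 90-98% |

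A second set (visits 0, 1, 4, 6, 12, 24; share 0.83; slope SDs 1.47 and 3.22; 24-month SD about 5.7) gives about 82% at 30% missing and 90% at 10% for 0.20 of the 24-month SD.

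**6. The .942.** At the 24-month standard error, 0.8 has noncentrality 2.996 × 0.8/1.2 = 1.998, or 52% power (67% with nothing missing). For .942 (noncentrality 3.532) to stand beside 85%, the within-treatment contrast needs [(0.8/3.532)/(1.2/2.996)]² = 0.32 of the 24-month variance. The model in 5(b) shows that this can happen, but the variances that produce it are not printed.

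**7. Time points.** Scheduled visits: baseline, 1, 4, 6, 12, 18, 24 and 30 months. That is 8 in all and 7 up to month 24; the simulation used 6. Power is labelled only as within treatment and as 24 months.

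**The case against.** The strongest defence is step 5(b): one shared set of variances gives all three headline figures, with the psychosocial range produced by the missingness that Section 9.2 says was varied. This stands as a demonstration that the figures can coexist. A reader might infer that 82-90% is false, that true power was 61%, or that the psychosocial variances must have differed from the BMI variances. The documents support none of these. The defence has limits, though. It scales 0.20 to an SD of about 5.7-5.8, where the only SD printed beside the 24-month effect is 4.5, and it overshoots the stated within-treatment range slightly.

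A reader might also infer that .942 is an error, because a smaller difference with the same SD gets higher power than 1.2. That does not hold: an earlier contrast in a growth model can be far more precise, and step 6 shows only that the text does not let anyone verify it.

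It might finally be said that neither primary time point has stated power. That goes too far. Within treatment most naturally covers month 6, since Section 9.1 ties the 6-month hypothesis to the end of intervention. Section 4.1 also counts 12 months of intervention, so the label should be defined. Month 12 is the clear gap.

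Recruitment has closed (footnote in Section 5.2), so nothing here can change N. That limits the remedy but does not make the printed power right.

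**Conclusion.** The point holds in this form: the 82-90% does not follow from what Section 9.2 prints. With 0.20 in units of the printed SD and the BMI precision, power is about 61% at 30% missing, 72% at 10% and at most 77%, assuming two-sided 5% and monotone dropout. Higher values need unprinted inputs, either smaller psychosocial variances or a larger SD unit, and the text does not say which applies. The .942 is unverifiable, not wrong. The 85% and the within-treatment 90-98% are not disputed. Month 12 has no stated power, and the 6 simulated time points match neither the full schedule nor the visits up to month 24. This should be fixed. Confidence is medium, because the simulation's inputs are not in the documents.

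**What to change.** Keep N=600 and the planned analysis. From the simulation records, or from a rerun on the actual visit schedule if they are lost:

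- State alpha and sidedness, and whether 4.5 is the SD of BMI or of BMI change.
- State the SD to which 0.20 is scaled, and the variance components for BMI and for the psychosocial scores.
- State which visits were simulated, the visit at which the within-treatment period ends, and what varies across each power range (missingness or outcome).
- Restate between-arm power, or the detectable difference, at months 6, 12 and 24.
- Replace 82-90% with the value that the stated inputs give. That is about 61% at 30% missing if 0.20 is in units of the printed SD with the BMI variances.
- Define which parameters are shared between the BMI and psychosocial calculations, or correct the phrase.

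The two-sample figures above are only a check and should not be entered as the planned model's power. The cost is retrieving or rerunning one simulation and rewording one paragraph. The downside is that the restated power may be less favourable, and it must be dated as made after recruitment closed.

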## 3 OBJECTIVES AND ENDPOINTS

OBJECTIVES	ENDPOINTS	JUSTIFICATION FOR ENDPOINTS
Primary		
To test the comparative efficacy of Noom Health vs. Noom Digital Health for weight loss, quality of life, psychosocial functioning, and self-reported health status.	We will conduct remote scheduled direct entry interview and self-report questionnaire data at 8 time points (Screening/Baseline, 1 month, 4 months, 6 months, 12 months, 18 months, 24 months, and 30	Hypothesis 1: Noom Health users will show 6 month efficacy relative to Noom Digital Health for weight loss at post-intervention.  Hypothesis 2: Noom Health users will show long-term (12 Month) efficacy relative to Noom Digital Health.

OBJECTIVES	ENDPOINTS	JUSTIFICATION FOR ENDPOINTS
	months). Weight data will be collected by video observed scale. Digital scales will be provided for those who do not have access.	
Secondary		
To compare potential moderators of treatment response in Noom Health vs. Digital Health subjects.	We will conduct remote scheduled direct entry interview and self-report questionnaire data at 8 time points (Screening/Baseline, 1 month, 4 months, 6 months, 12 months, 18 months, 24 months, and 30 months). Weight data will be collected by video observed scale. Digital scales will be provided for those who do not have access.	Hypothesis 1: Clinical Profile (composite moderator) will show significant interaction with treatment condition, demonstrating that individuals with a more severe profile (older, less support, more health conditions, more psychosocial problems) will benefit more from Noom Health than Digital Control.  Hypothesis 2: Weight suppression (absolute difference between highest and current weight) will moderate efficacy of Noom Health vs. Digital Education.
Tertiary/Exploratory		
To identify within treatment mechanisms of change among Noom Health group.		Hypothesis 1: Time series Bayesian belief network model of adherence will predict (a) study dropout, (b) successful weight loss, (c) quality of life.  Hypothesis 2: Regular eating will mediate treatment effects of weight loss over time.  Hypothesis 3: Self-efficacy of weight loss will mediate Noom Health vs. Noom Digital Health effects at post treatment and 12 month follow-up.

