#### 9.4.9 EXPLORATORY ANALYSES

We will utilize repeated measures Bayesian belief network to establish adherence within the Noom group and examine its changes to relationship over time. BBNs are most often used to establish greatest

predictive value related to available data and tested against randomly sampled (80-20) develop and test data sets.

Our Mediation model of weekly regular eating is a time series mediation model and assumes latent measure of meal-snack adherence will mediate changes in weight and included a time-varying set of latent variables that change in parallel to our primary outcome.

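### Exploratory Hypothesis 2 claims that regular eating mediates the treatment effect, but the analysis described names no path from randomised arm and no temporal order, so neither it nor its power figure answers the hypothesis

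*Combined protocol and SAP*

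**What the plan says.** Section 3, under the tertiary/exploratory heading, gives the objective as "To identify within treatment mechanisms of change among Noom Health group". Two mediation hypotheses sit beneath it. Hypothesis 2 reads "Regular eating will mediate treatment effects of weight loss over time". Hypothesis 3 reads "Self-efficacy of weight loss will mediate Noom Health vs. Noom Digital Health effects at post treatment and 12 month follow-up".

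Section 9.2 powers a time-series mediation model of weekly regular eating. It says "The calculation is based on effect size goal of .25, .5, and .75", without giving the metric, and reports that "power for the smallest effect size (.25) is approximately .80 with 10% missing data or less". The paths behind that figure are "moderate correlations between time and change in regular eating (.3) and moderate correlation between regular eating and weight outcome (.3". No arm effect on regular eating is listed.

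Section 9.4.9 describes the mediation model again, with a "time-varying set of latent variables that change in parallel to our primary outcome". It names no exposure, lag or indirect-effect estimand, and gives no model for Hypothesis 3.

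Two general statements also bear on the point. Section 9.2 opens with growth models that have treatment as the main predictor, and Section 9.3 says all analyses include everyone randomised. Neither is tied to the mediation model.

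**The concern.** A treatment effect in this trial is a contrast between two randomised arms. To say that eating mediates it, the analysis must show that arm changes eating and that eating then changes weight. The paths in Section 9.2 instead start from time. Within one arm there is no treatment contrast to decompose.

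Section 4.1 has participants in both arms logging eating episodes and tracking diet and weight, so regular eating may well change over time under control too. A significant time-to-eating-to-weight path would match the wording of Hypothesis 2 and could be reported as the mechanism of Noom Health, although nothing in it separates Noom Health from control. With no stated order in time, it would also leave open whether eating led weight or weight led eating.

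**Working it through.** **1. The plan's own figure.** Section 9.2 gives power of about .80 at effect size .25 with at most 10% missing. It does not state alpha, the number of weekly points, autocorrelation, factor loadings, analysis N or effect metric. Closed forms at two-sided alpha .05 (assumed):

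- Both paths at r = .3, n = 270 (300 × .9): atanh(.3) × √267 = 5.06; Φ(5.06 − 1.96) = .999 per path, .998 jointly. At n = 300 the joint value is .999.
- Two-arm difference d = .25, 270 per arm: .25/√(2/270) = 2.905; Φ(2.905 − 1.96) = .828.

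Neither gives .80. With so many inputs missing this is a failure to reproduce, not a shown error, and the point does not rest on it.

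**2. Why the two questions differ.** Write eating = γ·time + δ·(arm × time), and weight = b·eating. The path through time is γ × b; the path through arm is δ × b. With the plan's values and no arm effect (γ = .3, b = .3, δ = 0), the first is .3 × .3 = .09 on the standardised scale and the second is 0. The model can be right about γ and b and say nothing about δ.

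**3. Illustration.** Assumptions: 300 per arm, 24 weekly points, time-to-eating correlation .3, a true effect of eating on weight, no arm effect on eating, eating-to-weight path adjusted for time, 300 runs. The Noom-Health-only test (both paths significant) declared mediation in 100% of runs, including with person fixed effects. The arm-based test did so in 0 to 5%. No confounding is involved here; the single-arm model is answering another question.

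**4. What changing the exposure does not cure.** Now let eating have no effect on weight, with a shared engagement factor driving both (loading .55 on each), N = 600. The plain arm-based test is falsely significant in 69% of runs if the arm effect on eating is d = .20, and in 96% if d = .30. Randomising arm does not randomise eating.

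**5. Power with arm as exposure.** The documents give no arm effect on regular eating, so a range is needed. For 1:1 allocation, r = d/√(d² + 4). Power for the arm path is Φ(atanh(r) × √(N − 3) − 1.96). The eating-to-weight path at .3 has power of about 1.00 at these N, so the product equals the first term. Example, d = .20 and N = 540 (600 × .9): r = .0995; .0998 × √537 = 2.31; Φ(2.31 − 1.96) = .64.

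| d, arm on eating | N = 540 (10% missing) | N = 420 (30% missing) |
|---|---|---|
| .10 | .21 | .17 |
| .15 | .41 | .33 |
| .20 | .64 | .53 |
| .25 | .82 | .72 |
| .30 | .93 | .86 |

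**The case against.** The strongest reply is that time as exposure is inferred from one list of simulation inputs. Section 9.4.9 names no exposure and so does not exclude arm, Section 9.3 includes all randomised participants, and Hypothesis 3 compares arms under the same objective, so the Noom-Health-only heading is loose. All of that stands. It turns a wrong exposure into an unspecified one, and the same clarification is needed.

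It is also fair that parallel-process growth models can test mediation. They can when arm predicts the mediator's change and the order is specified. Parallel change is not a fault in itself; the missing arm path and order are.

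One might also read the .25 as an arm difference in SD units, which would give about .82 at N = 540, near the stated .80. The text does not say so, and the correlations it lists run from time.

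A reader might infer that the trial will almost certainly report false mediation. The documents do not support that. When eating has no effect on weight and a stable person-level engagement factor drives both, a pooled time-based regression is significant in 100% of runs, but a within-person regression adjusted for time is significant in only 5.5%. The protocol does not fix the estimator, and growth models ordinarily carry person-level intercepts.

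**Conclusion.** The mismatch holds. Hypothesis 2 is about a treatment effect; the only stated paths start from time, and no section supplies an arm path or a temporal order. A significant result from the analysis as described would not show that regular eating mediates the randomised effect, and the power of about .80 cannot be carried over to that claim. Illustrative arm-based power is .21 to .93 for d = .10 to .30, assuming an eating-to-weight correlation of .3, N = 540 and two-sided alpha .05.

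The conclusion does not extend to saying that the trial could never test mediation, or that making arm the exposure would by itself yield a causal answer. The hypothesis is exploratory, so the consequence is confined to what may be claimed about mechanism.

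**What to change.** In Sections 3, 9.2 and 9.4.9:

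- Define mediation for Hypotheses 2 and 3 in all randomised participants, with arm as the exposure.
- Measure the mediator before the outcome: regular eating from the app logs, or self-efficacy at months 1 and 4, with weight at months 6 and 12 as the outcome, adjusted for baseline weight.
- State the absence of unmeasured mediator-outcome confounding as an assumption, naming engagement as the obvious threat.
- Restate power for the arm-to-mediator path, with the assumed arm effect, alpha and N.
- Report the Noom-Health-only time series as a within-arm association.

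Adjustment for weight at the mediator visit can be an optional sensitivity analysis. That weight is measured after randomisation and may be affected by arm, so conditioning on it changes the estimand.

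The cost is wording: both arms log eating, and the Schedule of Activities has self-efficacy and weight at every visit. The price is that power for this aim will probably be lower than stated.
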